The study duration of 52 weeks was chosen for three reasons: 1) feasibility, 2) to maximize physiologic benefits of exercise, and 3) evidence from natural history studies suggesting individuals with preclinical AD have measurable changes in brain atrophy and cognition over 52 weeks. First, our experience suggests 12 months is achievable based on high retention and adherence rates to our 6-month intervention. Second, physiologic adaptations to exercise (VO₂, muscle mass) occur at 3-4 months consistently¹¹⁶ but it remains

unclear how long is needed for brain benefits. A meta-analysis of exercise³ suggests durations greater than 6 months are associated with more cognitive benefits and 52 weeks of exercise is associated with structural and functional brain change.^{77, 117} Third, early preclinical AD studies have observed decline in cognition and brain structure in 52 week longitudinal studies.⁷⁷ These expected changes in controls will enhance the study's power to observe exercise-related effects on AD pathophysiology and cognition. Thus, a 52 week intervention is feasible and will enhance the likelihood of observing exercise-related biological changes in the brain.

Aerobic Exercise Intervention

Upon successful completion of baseline evaluations, participants randomized to the aerobic intervention group will exercise 150 minutes over 3 to 4 days per week for 52 weeks with supervision in a local KUMC approved facility. Through our current trials, we have a strong relationship with the 14 greater Kansas City YMCAs (see letter of support) and several additional facilities with which we have a memorandum of understanding concerning conducting research. Each center is staffed by trained exercise personnel with experience in the older adult population and personal training certification through the National Commission for Certifying Agencies.

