Quality Assurance for Training and Data Collection: While a site is active, a member of the exercise intervention team makes site visits regularly to collect data forms, review quality of data collection (e.g., completeness and accuracy of data entry) and ensure competency in the standard application of the exercise protocol through observations of the exercise instructors. If procedural discrepancies are identified, these are then addressed with the instructors.

Safety: One trainer supervises a maximum of four participants at one time. If the participant is deemed a fall risk, the trainers are prepared to provide 1:1 supervisor to participant supervision. All of the treadmills are equipped with handrails and emergency stop switches. All of the trainers are Adult CPR certified and trained in the use of portable defibrillators which are available at all of the facilities.

Control Group

Standard-of-care education (SOC) – All study participants randomized to the control group will receive education from study staff about the importance of maintaining a healthy and active lifestyle. Each enrollee will receive our SOC education based on a standardized script along with standardized literature, “Exercise and Physical Activity: Your Everyday Guide from the National Institutes on Aging” and the “KUADC Promoting Healthy Brain Aging.” These booklets provide vetted and reliable information for older adults on how to exercise. Participants may ask questions of study staff at that time. Participants randomized to the control group will receive no further counseling on physical activity.

Aim 1: Determine the effect of aerobic exercise on amyloid burden in individuals with preclinical AD (cognitively normal with elevated cerebral amyloid) and those without elevated amyloid.

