Outcomes: Images will be evaluated qualitatively and quantitatively. Data will be submitted to Avid for qualitative analysis. Images will be visually examined by a trained radiologist or nuclear medicine physician who is blinded to the subject diagnosis and will be reported as either A β elevated (AD-like) or A β non-elevated (not AD-like). Qualitative interpretation will be performed in the following manner: the images will be reviewed using a black-white scale with maximum intensity of the scale set to the maximum intensity of all brain pixels. A elevated scan will have at least one area where the grey matter is more intense than adjacent white matter or at least 2 brain areas where the grey white contrast is reduced or absent. For quantitative evaluation, standard uptake values (SUV) will be calculated using SPM software in 6 cortical areas (frontal cortex, temporal cortex, parietal cortex, precuneus, anterior and posterior cingulate) and the cerebellum. SUV ratios (SUVR) for cortical target areas relative to the cerebellum will also be calculated and a global mean SUVR will be calculated from the average across all cortical target areas.

Statistical Analyses for Aim 1: This is a two-arm, 2:1 randomized, controlled clinical trial comparing 52 weeks of aerobic exercise to control intervention. Based on drop out rates from those who have completed our exercise trials (2 of 53 [4%] dropped out of the TEAM study and 1 of 11 [9%] dropped out of ADEPT), we conservatively estimate that 15% of the subjects will drop out of the study, leaving approximately 85 subjects for analysis. We will perform analyses based on intent-to-treat to maintain the benefits of the randomization. Per protocol analyses will also be conducted among the subjects that complete a minimum of 80% of their sessions. To further assess the response to aerobic exercise, we will conduct analyses that replace the primary explanatory factor (treatment group) with continuous measures of increase (change from baseline) in aerobic fitness (VO₂peak). This will allow us to assess the aerobic fitness hypothesis which states that aerobic fitness gains mediate neural benefits of exercise.

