Additionally, there are certain risks and discomforts that may be associated with exercise that include temporary shortness of breath, muscle fatigue, sweating, and physical discomfort. Muscles may be sore up to three days after performing the exercise. Also, there exists the possibility of an undiagnosed medical problem that may surface during the exercise. During testing, participants will be carefully observed by members of the research team to reduce these risks associated with exercise.

Adverse Events: Adverse events will be defined as any untoward medical occurrence in study participants or others immediately involved in the performance of the protocol, which does not necessarily have a causal relationship with the study treatment, but results in a change in intervention, daily function, hospitalization or rated category 3 or above using the National Cancer Institute Common Terminology Criteria for Adverse Events (CTCAE) v3.0.²⁰⁹ Expected events such as slight muscle soreness consistent with exercise, or those consistent with a participant's prior medical history not sufficient to alter the intervention will not be considered an AE. Staff involved in performance of the protocol (e.g. trainers, dieticians, coordinators) will continually monitor participants for adverse events throughout the intervention, and study staff will assess adverse events at every testing visit as well as during regularly scheduled telephone assessments with all randomized participants.

If study staff, tester, participant, caregiver or exercise instructor reports adverse events or complaints, relevant information will be collected and documented.

The participant will be evaluated by the unblinded investigator identified in the protocol. The investigator will have access to training logs, telephone assessment forms, and all study-related testing results. The

APEX Protocol 22 April 2016

investigator will determine the severity (according to the CTCAE) and relatedness of the AE to the intervention. The investigator will identify adverse events of clinical concern, those that may require further workup, or suggest that additional participation in the intervention might be a safety risk. These AEs will first be discussed with the participant and then communicated to the study staff or providers with participant's consent and as appropriate.

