An internal safety committee will meet quarterly to review adverse events and the overall safety of the ongoing trial. The committee will be composed of three clinicians: [name], [name], and [name]. The primary responsibilities of the DSMB are to 1) periodically review and evaluate the accumulated study data for participant safety, study conduct and progress, and efficacy when planned in the protocol, and 2) make recommendations to the PI concerning the continuation, modification, or termination of the trial.

Should a study participant experience an AE, relevant information will be collected and documented, and the AE will be reviewed by the appropriate investigator within 24 hours. If the investigator determines the AE is directly related to the study, raises concern about increased risk to the participant or overall safety of the study design, the safety committee will be notified within 24 hours. The DSMB will evaluate the AE and will make recommendations based on the protocol (e.g. stopping rules).

Women and Minority Inclusion in Clinical Research

Inclusion of women: Women are included in all studies described. We expect that approximately 50% of the subjects will be women.

Inclusion of minorities: All minority groups are encouraged to participate in this and all our research projects. We place an extra emphasis on the recruitment of minorities through the KU ADC and the Landon Center on Aging. The ADC Education Core recently hired a minority outreach coordinator to increase enrollment of African Americans into ADC studies. The Landon Center on Aging community outreach effort specifically targets the Hispanic and African American populations through activity in service agencies for these populations and with targeted advertising in minority publications. In 2003, the University of Kansas Medical Center's outpatient population was composed of 18% African-American, 10% Hispanic, 1% Asian, and 3% other. We expect this proportion of minorities will be reflected in our enrollment. All minority groups are encouraged to participate in the research projects.

REFERENCES

1. Middleton LE, Yaffe K. Targets for the prevention of dementia. *J Alzheimers Dis*;20:915-924.

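### The adverse-event definition is not arm-neutral, and its prior-history exclusion conflicts with its own hospitalisation and category 3 triggers

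*Combined protocol and SAP*

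**What the plan says.** The Adverse Events paragraph under Protection of Human Subjects sets the conditions for an AE. An untoward event qualifies if it is one that need not be causal "but results in a change in intervention, daily function, hospitalization or rated category 3 or above" on CTCAE v3.0. That gives four alternative triggers. Relatedness is not one of them, since the event is described as one "which does not necessarily have a causal relationship with the study treatment".

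The following sentence takes events out again. It begins with "Expected events such as slight muscle soreness consistent with exercise" and continues that "those consistent with a participant's prior medical history not sufficient to alter the intervention will not be considered an AE". It states no exception for hospitalisation, loss of daily function or category 3.

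The two arms differ in what there is to alter. Under Aerobic Exercise Intervention, "participants randomized to the aerobic intervention group will exercise 150 minutes over 3 to 4 days per week for 52 weeks with supervision". Under Control Group, controls get a scripted education contact and booklets, after which "Participants randomized to the control group will receive no further counseling on physical activity". Statistical Analyses for Aim 1 does describe the trial as "comparing 52 weeks of aerobic exercise to control intervention", so control carries the label of an intervention. Nowhere is it said what changing or altering that intervention would mean for a control.

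AE status decides what reaches oversight. The end of the Adverse Events text sends all AEs to the investigator, the coordinator, the DSMB and the Human Subjects Committee. The Data Safety and Monitoring Plan attaches 24-hour investigator review to AEs and asks the committee to "periodically review and evaluate the accumulated study data for participant safety" and to advise on continuing, modifying or ending the trial.

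**The concern.** A safety definition in a randomised trial should classify the same event in the same way in both arms. Here one trigger and one exclusion depend on something that continues in one arm only. Two consequences follow.

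First, lower-grade events that only disturb training are recorded on exercise and have no counterpart on control. Second, if the exclusion sentence prevails over the trigger sentence, serious events that fit a control's medical history stop being AEs, while the same events on exercise remain AEs whenever training is interrupted.

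Both push in the same direction: more AEs on exercise and fewer on control at equal true rates. The stakes are the safety counts that the committee sees, any AE table in the report, and whether some serious control events have a stated route to the committee at all.

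**Working it through.** There is no stated figure to reproduce, so the check sets the two sentences against each other, placing the same event in each arm.

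Notation, each item yes or no: I = alters an ongoing intervention; F = changes daily function; H = hospitalisation; G = CTCAE category 3 or above; P = consistent with prior medical history.

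- Inclusion (first sentence): I or F or H or G.
- Prior-history exclusion (second sentence): P and not I.
- Assumption: I = yes on exercise, meaning the event does disturb training; I = no on control, because nothing is ongoing.

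F, H, G and P give 2 × 2 × 2 × 2 = 16 profiles, of which 8 involve hospitalisation.

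**Literal reading (the exclusion overrides).** On exercise I = yes, so every profile is included and none is excluded: 16 of 16. On control an event counts only if at least one of F, H, G holds and P does not: (8 − 1) × 1 = 7 of 16. The arms disagree in 16 − 7 = 9. Among the 8 hospitalisation profiles, control counts the 4 with P = no, so the arms disagree in 4, all consistent with prior history.

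**Lenient reading (the exclusion reaches only events with none of F, H, G).** Exercise still counts 16. Control counts every profile with at least one of F, H, G: 7 × 2 = 14. The arms disagree in 16 − 14 = 2, and in 0 of 8 with hospitalisation. The first sentence taken alone gives the same result.

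| Reading | Exercise | Control | Disagree | Disagree, hospitalised |
|---|---|---|---|---|
| Literal | 16 | 7 | 9 of 16 | 4 of 8 |
| Lenient | 16 | 14 | 2 of 16 | 0 of 8 |
| Three neutral triggers only | 14 | 14 | 0 of 16 | 0 of 8 |

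The two profiles that disagree on every reading are the training-only events: no function change, no hospitalisation, below category 3, with or without prior history.

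These are logical cases, not frequencies. No event rates are given, so the size of the imbalance cannot be derived. If training-only events added a fraction x to an otherwise equal AE rate on exercise, the recorded rate ratio would be 1 + x: 1.05 at x = 5%, 1.5 at 50%, 2.0 at 100%. That restates the assumed x and is illustrative only.

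**The case against.** Several points on the other side are sound.

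- A reader might infer that the definition as a whole turns on the intervention. It does not: three of the four triggers apply equally in both arms.
- A reader might infer that any hospitalisation could be an AE on exercise and not on control. The trigger sentence names hospitalisation in its own right, so this follows only for admissions that fit prior history, and only if the exclusion overrides. The exclusion sentence opens with slight soreness and can be read as meant for minor expected complaints. That reading is reasonable, but the text does not state it.
- A reader might infer that serious control events go unrecorded. The same section says reported events and complaints are documented, testing visits and telephone assessments cover all randomised participants, and Telephone Checks include medical history and medication changes. The institutional reporting policies cited there are not available here and may catch such events. What can be said is that an event classed as not an AE has no route to the DSMB stated in this document.
- The analysis sections contain no between-arm AE test, so any false-positive rate would describe a test the plan does not have.
- Assuming I = yes for every exercise event is a simplification. Adherence and Retention expects several missed sessions, so a short interruption might not be called a change; where it is not, the arms agree. An injury that stops training will also often affect daily function, making it an AE in both arms.
- A lower reporting threshold in the exposed arm is a defensible caution, and removing that trigger would take training injuries out of DSMB reporting.

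These points narrow the concern and shape the fix. They do not remove the training-only asymmetry, or the conflict between the two sentences.

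**Conclusion.** The definition is not arm-neutral. On any reading, a lower-grade event that changes training but not daily function is an AE on exercise only (2 of 16 profiles). On the literal reading, a control's hospitalisation or category 3 event consistent with prior history is also not an AE, while the same event on exercise is one if it interrupts training (9 of 16 profiles in all, 4 of 8 with hospitalisation). The two sentences conflict on this and must be reconciled.

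This rests on two assumptions: that controls have nothing ongoing to alter, which is a strong inference from Control Group rather than a stated fact, and that the exercise-arm event does alter training. The effect is on safety counts and on what reaches the committee, not on power, sample size or any efficacy analysis. Its direction is clear; its size cannot be given from the documents.

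**What to change.** 1. State that the expected-event and prior-history exclusion applies, in either arm, only to events that do not change daily function, cause hospitalisation or reach CTCAE category 3.
2. Keep events that change the exercise programme as reportable AEs, so nothing now sent to the DSMB or the Human Subjects Committee is lost.
3. Add a data field flagging AEs that qualify on that trigger alone.
4. Base any between-arm AE summary on the three arm-neutral triggers, and show the flagged events separately for the exercise arm.

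The cost is protocol wording, one REDCap field and a few more recorded events that fit prior history. Because this is Amendment 4 and at least 84 non-elevated participants had already been screened, the revised wording would also have to be applied to any events already classified. No extra visits or staff are needed.
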